6.10.3.5. Most Common Adverse Events

The most common TEAEs, determined as TEAEs occurring in $\geq 5\%$ in any LY3298176 arm, will be summarized by SOC, PT, and treatment group. This summary will also include the number of such events by SOC, PT, and treatment group.

6.10.3.6. Deaths

All deaths recorded on the status page, the AE page, or the SAE page (with a death date, cause of death, outcome, or SAE categorization present) of the case report forms (CRFs) will be considered a death for summary purposes. All deaths (CV or non-CV) that occur during the treatment period or follow-up period will be adjudicated by an independent central adjudication committee in compliance with a study-specific adjudication charter. Results of the adjudication will be entered in the death adjudication electronic case report page (eCRF) page.

A listing of adjudicated results will include the adjudicator assessment of death type, whether or not the adjudicator’s assessment of the event date agrees with the investigator’s assessment of the event date, and the date of the event, showing the adjudicator’s assessment in the case of non-agreement. If adjudicated results show >1 death per treatment group or >3 deaths within any 1 treatment group, a summary table will present patient incidence of deaths by SOC, PT, and treatment group.

6.10.4. Adverse Events of Special Interest

Adverse events of special interest to be identified and described during this study are injection site reactions, hypersensitivity reactions, hypoglycemia, acute pancreatitis, major adverse CV events, and selected GI events (nausea, vomiting, and diarrhea).

Descriptive statistics for AESIs will be presented by treatment group and visit. Continuous responses will be summarized using sample size, mean, SD, median, minimum and maximum, while categorical responses will be summarized using sample size, frequency, and percentage.

In addition, for AESIs with information collected on the AE eCRF page (that is, hypersensitivity reactions, acute pancreatitis, and major adverse CV events) summary tables will be presented only if $>3\%$ of patients have the AESI. The incidence of patients with at least 1 AESI and the

patient incidence of AESIs will be summarized, showing frequency and percentage of patients, by SOC (if applicable), PT, and treatment group. The total number of AESIs and the number of AESIs for each SOC (if applicable) and PT will also be reported for each treatment group.

Listings by patient will be provided for AESIs. Listings will also present adjudication information by patient for adjudicated events.

6.10.4.1. Hypersensitivity Reactions

A listing of potential hypersensitivity reactions will be provided. For the purpose of this listing, any event satisfying any one of the Anaphylaxis reaction standard Medical Dictionary for Regulatory Activity (MedDRA) queries (SMQs), Hypersensitivity SMQs, or Angioedema SMQs will be included. Summary tables will be presented only if the number or nature of the events warrants such a comparison.

6.10.4.2. Injection Site Reactions

Injection site reactions are collected in a questionnaire. The following items or other available categories may be collected and summarized for each injection site reaction:

- pain
- itching
- rash
- reaction timing
- swelling
- redness
- erythema
- bruising
- hematoma

Injection site reactions which meet SAE criteria will also be collected as AEs. If >3% patients have such an event occur, then these injection site reactions may be summarized by PT using the version of MedDRA current at the time of programming.

6.10.4.3. Nausea, Vomiting, and Diarrhea

Nausea, vomiting, and diarrhea event information will be collected on a designated separate eCRF page. Summaries and analyses for incidence will be provided for each randomized treatment group and by visit.

The prevalence and incidence of nausea, vomiting, and diarrhea will be summarized by the treatment and the time interval of interest. In addition, similar tables will also be generated by actual dose and time interval. The duration of each event will also be computed in days as event stop date minus event start date. For computation purposes, events that are ongoing will be considered censored (that is, ended) at the date of last study contact.

The maximum severity and duration from baseline to Week 12 of nausea, vomiting, and diarrhea will be summarized by treatments.

Plots with the percentage number of subjects with the events versus initiation time course will also be generated. The y-axis is the percentage of subjects with the specified AE and the x-axis is the time since the first dose.

A listing with GI TEAEs of interest will be provided.

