5.1. Overall Design

Study GPGF is a randomized, multicenter, placebo-controlled, double-blind, parallel arm, Phase 2 titration study in T2DM patients who have inadequate glycemic control with diet and exercise with or without a stable dose of metformin monotherapy. The study is designed to measure the change in HbA1c at the end of study treatment compared with placebo. These data will support dose selection and the optimal titration scheme that minimizes GI-related AEs for Phase 3 trials. The study will consist of 3 treatment periods: approximately 1-week lead-in period, followed by a 3-month treatment period, and a 4-week safety follow-up period (see [Figure GPGF.1](#)). A double-dummy dose administration scheme will be employed to ensure patients and investigators (as well as sponsor study team and monitors) remain blind to the LY3298176 and placebo treatment assignments within each titration group.

[figure not shown]

Figure GPGF.1. Illustration of study design for clinical protocol I8F-MC-GPGF.

Study Period I (Screening and Lead-In):**Screening (Visit 1)**

Throughout the study, patients treated with metformin will remain on the same dose they were receiving at Visit 1 unless changes need to be made for safety reasons. All patients will be encouraged to maintain their prestudy diet and exercise levels through the course of the study.

The purpose of screening procedures at Visit 1 is to establish initial eligibility (see Section 6) and to obtain blood samples for laboratory assessments needed to confirm eligibility. Patients who meet all applicable inclusion criteria and none of the applicable exclusion criteria at Visit 1 will continue on to Visit 2.

Lead-In (Visit 2 to Visit 3)

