9.2.1.2.1. Nausea, Vomiting, and Diarrhea

Nausea, vomiting, and diarrhea events will be recorded on a specific eCRF. They should not be recorded as AEs unless the event meets an SAE criterion. For each event, assessment of severity, duration, and investigator's opinion of relatedness to study drug and protocol procedure will be captured.

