10.3.4.6. Adverse Events of Special Interest

Hypoglycemia, hypersensitivity reactions, injection site reactions, acute pancreatitis, major adverse CV events, and selected GI events such as nausea, vomiting, and diarrhea, are defined as AESIs.

Descriptive statistics for the AESIs will be presented by treatment group and visit. Continuous responses will be summarized using sample size, mean, SD, median, minimum, and maximum, whereas categorical responses will be summarized using frequencies and percentages.

Summaries and analyses for incidence, time to onset, duration, and severity of GI events (nausea, vomiting, and diarrhea) will be provided for each treatment group during the 12-week treatment period and by visit. The planned reports will be detailed in the statistical analysis plan.

Additional analyses will be performed if necessary.

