4.2. Secondary Objectives

The secondary objectives are to compare each titration scheme to placebo at 3 months for the following secondary efficacy parameters:

- proportion of patients achieving HbA1c target of <7.0%
- the change in fasting blood glucose (FBG) (central laboratory) from baseline
- the change in body weight from baseline
- the change in waist circumference from baseline
- incidence of treatment-emergent adverse events (TEAEs) and serious adverse events (SAEs)
- incidence of nausea, vomiting, and diarrhea
- discontinuation of study drug due to adverse events (AEs)
- incidence and rate of hypoglycemia (severe, total, documented symptomatic, and nocturnal)
- incidence of anti-LY3298176 antibodies

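### Ongoing nausea, vomiting and diarrhea events are averaged as if they had ended, which shortens durations mainly for patients who leave early; same-day events also print as 0 days

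*SAP*

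**What the plan says.** SAP 6.10.4.3 gives one rule for events with a stop date: "The duration of each event will also be computed in days as event stop date minus event start date". It gives another for events without one: "events that are ongoing will be considered censored (that is, ended) at the date of last study contact". The reporting sentence is: "The maximum severity and duration from baseline to Week 12 of nausea, vomiting, and diarrhea will be summarized by treatments". The section names no time-to-event method, no flag for ongoing events and no count of them by arm.

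The parent section, SAP 6.10.4, describes continuous responses for adverse events of special interest by sample size, mean, SD, median, minimum and maximum.

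Protocol 10.3.4.6 commits to duration among the GI outputs: "Summaries and analyses for incidence, time to onset, duration, and severity of GI events (nausea, vomiting, and diarrhea) will be provided". Protocol 9.2.1.2.1 puts these events on a dedicated form rather than the adverse event form, unless they are serious. It lists what is captured ("For each event, assessment of severity, duration", among other items) and does not mention clock times.

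The GI measure listed as a secondary endpoint in SAP 4.2 is "incidence of nausea, vomiting, and diarrhea". In the protocol's Schedule of Activities (Section 2), Visit 10 falls on Day 84 and Visit 801 on Day 105. A patient who leaves early has an early termination visit as the final visit (Protocol 5.1).

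**The concern.** Censored and ended are opposite statements about a duration. A censored duration is a lower bound; an ended one is complete. The SAP equates the two and then plans summaries that have no way of handling a lower bound. A patient who leaves while still nauseated contributes a short, apparently finished event.

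The trial is meant to help find the "optimal titration scheme that minimizes GI-related AEs for Phase 3 trials" (Protocol 5.1). If one titration scheme loses more patients with symptoms unresolved, its mean and median durations would look better than they are. Non-serious events of these three kinds are kept off the adverse event form, so this SAP section is where their duration is analyzed.

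Two smaller gaps sit beside this. The date difference gives 0 for any event that starts and stops on the same date. And the summary window ends at Week 12 while ongoing events are counted to last contact.

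**Working it through.** The plan states no figure for GI event duration, so there is none to reproduce.

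**Inputs from the documents.** Visit 10 on Day 84 and Visit 801 on Day 105 (Protocol Section 2); 92 patients in four arms, so 23 per arm, with 13% dropout (Protocol 10.1); duration rules as in SAP 6.10.4.3.

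**Assumptions, not in the documents.** Durations T are exponential with mean m; onset is uniform over the time on study; an early leaver is last seen on Day 28.

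**Step 1: ongoing events.** With onset uniform on Days 0 to H and last contact on Day L, the SAP value is the smaller of T and (L − onset). Its expected value is m × (1 − p), where

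p = (m/H) × [exp(−(L − H)/m) − exp(−L/m)].

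Here p is both the share of events still ongoing and the proportion by which the mean is too low.

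| True mean m (days) | Completer, H = 84, L = 105 | Leaver, H = L = 28 | Completer cut at Week 12, H = L = 84 |
|---|---|---|---|
| 2 | 0.0% | 7% | 2.4% |
| 5 | 0.1% | 18% | 6.0% |
| 10 | 1.5% | 34% | 11.9% |
| 20 | 8.2% | 54% | 23.5% |

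Example, m = 10:
- Leaver: (10/28) × [1 − exp(−2.8)] = 0.357 × 0.939 = 0.335, so a true mean of 10 days is reported as about 6.6.
- Completer: (10/84) × [exp(−2.1) − exp(−10.5)], about 0.015.

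**Step 2: effect on an arm.** 13% of 23 is 3 patients. If those 3 are last seen on Day 28 and every patient contributes the same number of events, the arm-level shortfall is (20 × completer value + 3 × leaver value)/23. For m = 10 this is (20 × 1.46 + 3 × 33.5)/23 = 5.6%. For m = 2, 5, 10 and 20 the results are about 1%, 2%, 6% and 14%. An arm with no early leavers has 0%, 0.1%, 1.5% and 8.2%. At m = 10 the gap between two such arms is about 4 percentage points, or 0.4 day. Patients who leave because of a GI event have it ongoing more often than uniform onset implies, so the gap could be larger.

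**Step 3: the day count.**
- Inclusive calendar days are stop − start + 1, so events of 1, 2, 3 and 5 inclusive days are recorded as 0, 1, 2 and 4.
- As elapsed time the formula is right on average. If onset falls at a uniform time of day U, the date difference is floor(U + T), whose mean is the mean of T. True means of 0.5, 1, 3 and 5 days return 0.5, 1, 3 and 5, and adding 1 gives 1.5, 2, 4 and 6. With onset confined to 07:00 to 23:00, simulated means are 0.59, 1.11, 3.12 and 5.12.
- The share recorded as 0 days under uniform onset is 1 − m × [1 − exp(−1/m)]: 57%, 37%, 15% and 9% for means of 0.5, 1, 3 and 5 days.
- Between arms, inclusive means of 3 and 5 days become 2 and 4. The difference is 2 either way; the ratio moves from 5/3 = 1.67 to 4/2 = 2.0.

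**Step 4: the window.** For a completer, last contact is 105 − 84 = 21 days after the end of the Week 12 window. The SAP does not say whether those days count.

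**The case against.** The strongest reply is that little of consequence depends on this. Duration is descriptive, and SAP 6.10.3 rules out statistical tests of adverse event rates. Incidence, prevalence by interval, tables by actual dose, maximum severity and the time-course plots do not use the duration formula, and prevalence by interval captures lasting symptoms in another way. Patients who stop study drug for an adverse event are asked to stay in the study (Protocol 5.1 and 8.1.1), completers are followed three weeks past Visit 10, and planned dropout is about 3 per arm. This stands, and it limits the size of the point. It does not make a lower bound a complete value for those who do leave.

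A second reply is that stop minus start is a legitimate elapsed-time convention and that SAP 6.6 also omits a +1 for exposure. The first half stands. The exposure formula is weak support, because it adds the 7-day dosing interval: twelve weekly doses give 77 + 7 = 84 days, already a full count.

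A third reply is that Kaplan-Meier medians of events have their own difficulties, since one patient can have several correlated episodes and arms are small. That is fair. Censoring is also likely to be informative when patients leave because of the symptom. Both are reasons to show the count of ongoing events whatever method is used.

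**Conclusion.** The point holds as a cheap improvement. SAP 6.10.4.3 enters incomplete durations as complete, and no other section corrects this. The bias is downward relative to the true event length. It is small for completers followed to about Day 105 and larger for patients who leave early, and it could differ between arms if early departures do. The sizes rest on assumed exponential durations, uniform onset and a Day 28 departure; only the visit days, arm size and dropout rate come from the documents.

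Stronger readings are tempting, and the documents do not support them:

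- A reader might infer that durations are understated by 100%, 50%, 33% or 20% for events of 1, 2, 3 or 5 days. That holds only against an inclusive day count, which the SAP never promises.
- A reader might infer that the formula distorts the choice between titration schemes. For completed events it shifts every arm by the same day and leaves differences unchanged. The zero is a display problem.
- A reader might infer that a key endpoint is affected. The listed GI endpoint is incidence.
- A reader might infer that every reported duration is too short. Against the stated Week 12 window, counting to last contact can instead add up to 21 days.

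**What to change.** Amend SAP 6.10.4.3 in four places:

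1. Report the number and percentage of events, and of patients, with nausea, vomiting or diarrhea ongoing at the cut-off, by arm.
2. Summarize duration with a method that treats ongoing events as censored, such as Kaplan-Meier, and state how repeated episodes within a patient are handled. Alternatively, summarize resolved events separately and list the ongoing ones. Delete the gloss that equates censored with ended.
3. Define the day count: either stop − start + 1, labelled as calendar days, or stop − start, labelled as elapsed days with same-day events shown as <1 day.
4. Use one cut-off, Week 12 or last contact, for both the summary window and ongoing events. If Week 12 is chosen, more completers' events will be incomplete (last column of the Step 1 table), so item 2 matters more.

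The cost is a few sentences and slightly more table work, with no new data, since the existing rule already needs start dates, stop dates and ongoing status. The one trade-off is that adding 1 overstates elapsed time for very brief events; the <1 day display avoids this.

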6.10.4.4. Hypoglycemic Episodes and Total Hypoglycemia

Hypoglycemic episodes will be defined as follows: documented symptomatic hypoglycemia, asymptomatic hypoglycemia, probable symptomatic hypoglycemia, nocturnal hypoglycemia, and severe hypoglycemia. Total or overall hypoglycemia is defined as any event meeting the criteria for documented symptomatic hypoglycemia, asymptomatic hypoglycemia, or probable symptomatic hypoglycemia:

- **Documented Symptomatic Hypoglycemia:** Any time a patient feels that he/she is experiencing symptoms and/or signs associated with hypoglycemia and has a plasma glucose level of ≤ 3.9 mmol/L (≤ 70 mg/dL).
- **Asymptomatic Hypoglycemia:** An event not accompanied by typical symptoms of hypoglycemia, but with ≤ 3.9 mmol/L (≤ 70 mg/dL) plasma glucose.
- **Severe Hypoglycemia:** An episode requiring the assistance of another person to actively administer carbohydrate, glucagon, or other resuscitative actions. These episodes may be associated with sufficient neuroglycopenia to induce seizure or coma. Plasma glucose measurements may not be available during such an event, but neurological recovery attributable to the restoration of plasma glucose to normal is considered sufficient evidence that the event was induced by a low plasma glucose concentration.
- **Nocturnal Hypoglycemia:** Any hypoglycemic event that occurs between bedtime and waking.
- **Probable Symptomatic Hypoglycemia:** An event during which symptoms of hypoglycemia are not accompanied by a plasma glucose determination (but that was presumably caused by a plasma glucose concentration ≤ 3.9 mmol/L [≤ 70 mg/dL]).
- **Total or Overall Hypoglycemia:** Any event meeting the criteria for documented symptomatic hypoglycemia, asymptomatic hypoglycemia, or probable symptomatic hypoglycemia.

Information will be collected on the eCRFs to allow for classification of hypoglycemic episodes into these categories. Note that there is possible overlap among the categories, meaning that it is possible for a single event to have >1 classification.

A monthly rate of episodes per patient will be computed by visit, with 1 month defined as a 30-day period. At each applicable visit, the total number of episodes since the previous visit and the number of days since the previous visit will be determined. The monthly rate of episodes will be calculated as the total number of episodes divided by the number of days since the

previous visit and multiplied by 30 days. An overall monthly rate will be determined as the total number of episodes over all visits divided by the total number of days between all visits and multiplied by 30 days.

The monthly rate of episodes per patient by visit and overall will be computed for episodes of total hypoglycemia and episodes of nocturnal hypoglycemia. These rates will be summarized by treatment for each visit and overall.

The incidence of hypoglycemic episodes during a time period is defined as the number of patients experiencing at least 1 hypoglycemic episode within that time period. The incidences of total hypoglycemic, nocturnal hypoglycemic episodes and severe hypoglycemic episodes will be determined at each visit (that is, for the time period since the previous visit), and overall (that is, for the time period from first dose of study treatment to last study visit while on study treatment). The incidences for total and nocturnal hypoglycemic episodes will be summarized by treatment for each visit and overall using descriptive statistics (that is, sample size, frequency, and percentage); if a sufficient number of severe hypoglycemic episodes are reported, then incidence of these episodes will also be summarized.

Listings of hypoglycemic episodes of all types will be presented by visit for each patient.

Hypoglycemic episodes occurring after a patient discontinues treatment will be counted in the determinations of rate or incidence of episodes.

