6.3. Analysis Populations and Datasets

Three patient populations are defined for the analyses in this study with detailed information listed in [Table 6.1](#). Analyses datasets specifying data exclusion are listed in [Table 6.2](#).

Unless otherwise specified, listings will include FAS for all randomized patients; safety analyses, except for hypoglycemia events, will be conducted in the mITT population with the FAS; and efficacy analyses including primary and key secondary efficacy analyses will be conducted in the mITT population with the EAS.

Table 6.1. Analysis Populations

Population	Definition
All Entered	All patients who signed informed consent forms (ICFs)
All randomized (Intent-to-Treat [ITT])	All patients who were randomized to a treatment arm
Safety Population (Modified Intent-to-Treat [mITT])	All randomized patients who have taken at least 1 dose of the study medication. This is different from what is stated in the protocol. Analyses using the mITT population will be presented by the planned treatment group.

Table 6.2. Analyses Datasets

Analysis Dataset Name	Description
Full Analysis Set	All data available
Efficacy Analysis Set	Only include data on study medication without using rescue medication, i.e., excluding data after rescue medication initiation or after study treatment discontinuation (last dose date +7).

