6.10. Safety Analyses

Safety analyses will be classified by the actual titration treatment group. Safety descriptive statistic summaries may also include all LY3298176 doses combined, if appropriate. Unless specified otherwise, safety listings will display values/events during all study periods; AEs summaries will be presented for all postbaseline data. For some key summary tables, data will be presented both for the treatment period only and for the treatment period and follow-up period combined, if applicable.

For each patient, treatment period is defined as the date of first treatment dose to last treatment dose date +7 day.

Safety measures will include extent of exposure, vital signs, physical characteristics, TEAEs (including SAEs), adverse events of special interest (AESIs; that is, injection site reactions, hypersensitivity reactions, hypoglycemia episodes, gastrointestinal [GI] events [nausea, vomiting, and diarrhea], acute pancreatitis, and major adverse cardiovascular [CV] events), laboratory measures (including hematology, chemistry, urinalysis, and samples collected for testing for anti-LY3298176 and antibodies), and electrocardiograms (ECGs).

The summary statistics for continuous variables will be sample size, mean, SD, median, minimum, and maximum. If applicable (for example, in the case of MMRM analyses) these descriptive statistics may also include LS means, LS means standard error (SE), and 95% CI for each treatment group, as well as for LY3298176 difference from placebo.

The summary statistics for categorical variables will be sample size, frequency, and percentage.

Additional analyses, such as concentration-safety laboratory plots, may be performed, if warranted, upon review of the data.

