Appendix 1. Schedule of Events

Study Phase	Screen	Lead-In	Randomize	Treatment							Follow-Up	Early Term.
Visit	1	2	3	4	5	6	7T ^a	8	9T ^a	10 ^b	801 ^d	ET
Week of Treatment	-2	-1	0	1	2	4	4	8	8	12	(15)	
Study Day/(dose number)			0/(1)	7/(2)	14/(3)	28/(5)	31-34	56/(9)	59-62	84	105	
Visit Window (days)		+7	0	0	±2	±3		±3		±3	±3	
Administrative												
Informed consent	X											
Diabetes medical history/therapy	X											
Inclusion/exclusion	X	X	X									
Preexisting conditions	X											
Randomization			X									
IWRS	X	X	X	X	X	X		X		X	X	X
BG meter/supplies, if needed		X										
BG meter, instructions		X										
Diet, exercise, BG counseling		X										
Study diary, dispense		X	X	X	X	X		X		X		
Review patient diaries for BG values, AEs, hypoglycemic or hyperglycemic events		X	X	X	X	X		X		X	X	X
Subcutaneous injection training		X	X	X	X	X		X				
Study drug and injection supplies, dispense			X	X	X	X		X				
Health habits (alcohol use, tobacco use current/past)	X											
Patient returns study drug vials						X		X		X		
Study drug, assess compliance			X	X	X	X		X		X		
Patient Demographics												
Age	X											
Gender	X											
Race/ethnicity	X											

Study Phase	Screen	Lead-In	Randomize	Treatment							Follow-Up	Early Term.
Visit	1	2	3	4	5	6	7T ^a	8	9T ^a	10 ^b	801 ^d	ET
Week of Treatment	-2	-1	0	1	2	4	4	8	8	12	(15)	
Study Day/(dose number)			0/(1)	7/(2)	14/(3)	28/(5)	31-34	56/(9)	59-62	84	105	
Visit Window (days)		+7	0	0	±2	±3		±3		±3	±3	
Clinical Variables												
Physical examination ^c	X											
Height	X											
Weight	X		X			X		X		X	X	X
Waist circumference	X		X			X		X		X	X	X
Vital signs (BP and PR)	X	X	X	X	X	X		X		X	X	X
Antidiabetic medication	X	X	X	X	X	X		X		X	X	X
Concomitant medication	X	X	X	X	X	X		X		X	X	X
Other												
ECG ^e	X ^e		X			X		X		X	X	X ^e
Evaluation of injection site reactions			X	X	X	X		X		X	X	X
Collect AEs	X	X	X	X	X	X		X		X	X	X
Diagnostics (Safety)												
Screening laboratory tests ^f	X											
Pregnancy test ^g	X		X ^g									
FSH ^h	X											
Chemistry panel	X		X							X	X	X
Lipid panel	X		X							X	X	X
Lipase and amylase	X		X			X		X		X	X	X
eGFR	X											
Hematology	X		X							X	X	X
Urinalysis	X		X							X	X	X

Study Phase	Screen	Lead-In	Randomize	Treatment							Follow-Up	Early Term.
				4	5	6	7T ^a	8	9T ^a	10 ^b		
Visit	1	2	3	4	5	6	7T ^a	8	9T ^a	10 ^b	801 ^d	ET
Week of Treatment	-2	-1	0	1	2	4	4	8	8	12	(15)	

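### SAP 6.10.4.4 gives two incompatible windows for overall hypoglycemia incidence, SAP 6.3 names no dataset that would settle it, and three summaries of a listed secondary endpoint are not planned

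*SAP*

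**What the plan says.** **Window.** SAP 6.10.4.4 determines overall incidence "for the time period from first dose of study treatment to last study visit while on study treatment". Protocol 10.3.4.7 likewise defines incidence over a period on treatment. The last sentence of SAP 6.10.4.4 reads: "Hypoglycemic episodes occurring after a patient discontinues treatment will be counted in the determinations of rate or incidence of episodes".

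**Dataset.** SAP 6.3 states that "safety analyses, except for hypoglycemia events, will be conducted in the mITT population with the FAS". It then names no population or dataset for hypoglycemia, and neither SAP 6.10 nor 6.10.4.4 supplies one. Only listings have a default that covers hypoglycemia (the FAS, all randomized patients). SAP Table 6.2 defines just two datasets: the FAS, which holds all available data, and the EAS, which drops data after the start of rescue or more than 7 days after the last dose.

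**Endpoint.** SAP 4.2 and Protocol Table GPGF.2 list incidence and rate of hypoglycemia for four categories: total, nocturnal, severe and documented symptomatic. SAP 6.10.4.4 plans rates for total and nocturnal episodes and incidence for the same two. It summarizes severe incidence only if enough episodes are reported, without giving a number.

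**The concern.** The design produces the patients for whom the two window statements diverge. Missing two or more doses means permanent discontinuation of study drug (Protocol 7.6, 8.1.1 and 8.1.2). Such patients are meant to stay in the study if possible (8.1.1), and rescued patients are asked to complete all visits (5.1). After stopping, patients may start other standard diabetes treatment (8.1.2). Their later hypoglycemic episodes may therefore occur on another therapy. One sentence counts those episodes in overall incidence and the other leaves them out. Two careful programmers could report different figures from the same data, each following the SAP.

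The second stake is completeness. Hypoglycemia is a listed secondary endpoint, and a team that followed SAP 6.10.4.4 exactly would not tabulate three of its components.

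**Working it through.** The plan states no figure here to reproduce. The check lays the windows on the visit calendar, then crosses the listed endpoint with the planned summaries.

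**Step 1: inputs.** Visit days come from SAP Appendix 1 and Protocol Table GPGF.1: Visit 6 = day 28, telephone Visit 7T = days 31–34, Visit 8 = day 56, Visit 10 = day 84, Visit 801 = day 105. Dosing is weekly from day 0, so dose *k* falls on day 7 × (*k* − 1). The EAS limit is last dose + 7 days (SAP Table 6.2). Each arm has 23 randomized patients (Protocol synopsis).

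**Step 2: a constructed patient.** The last dose is Dose 7, on day 7 × 6 = 42. The patient stays to Visit 801, and the only hypoglycemic episode is on day 60. The EAS cut would be 42 + 7 = day 49.

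| Rule | Window closes | Day-60 episode |
|---|---|---|
| Overall-incidence definition | Visit 6, day 28 (or Visit 7T, days 31–34, if a telephone visit counts) | not counted |
| EAS, if that dataset is meant | day 49 | not counted |
| Closing sentence of 6.10.4.4 | day 84, or day 105 with Visit 801 | counted |

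Whether treatment is taken to end on day 42 or day 49, the last site visit within it is Visit 6, because Visit 8 is not until day 56.

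**Step 3: size.** If the last on-treatment visit is Week 4, follow-up to Visit 801 adds 105 − 28 = 77 days. If it is Week 8, it adds 105 − 56 = 49 days. One patient whose only episode falls in that gap changes a 23-patient arm's overall incidence by 1/23 = 4.3 percentage points.

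**Step 4: what is not in conflict.** By-visit incidence covers the time since the previous visit, and SAP 6.10.4.4 puts no on-treatment limit on it. The overall monthly rate uses the "total number of episodes over all visits divided by the total number of days between all visits", multiplied by 30, so episodes and days are taken over the same visits. Neither collides with the closing sentence.

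**Step 5: endpoint against plan.** Four categories × two measures = 8 summaries.

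| Category | Incidence | Rate |
|---|---|---|
| Total | planned | planned |
| Nocturnal | planned | planned |
| Severe | only if enough episodes | not planned |
| Documented symptomatic | not planned | not planned |

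Four are planned outright, one is conditional and three are not planned: 4 + 1 + 3 = 8. Protocol 10.3.4.7 has the same pattern, so the SAP carries over a gap already in the protocol's analysis section.

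**The case against.** **The window can be read another way.** Being on study treatment could mean the treatment phase, whose last visit is Visit 10 (Protocol 5.1). The day-60 episode would then count under both statements, and only the 105 − 84 = 21 days up to Visit 801 would remain in question. This is the best reconciling reading, but SAP 6.10 weakens it: there the treatment period is defined patient by patient, from first dose to last dose + 7 days. The wording still has to be settled.

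**The endpoint is better covered than the table suggests.** The count of eight comes from crossing a list; the documents do not state it. SAP 6.10.4 promises descriptive statistics for adverse events of special interest, which include hypoglycemia, and 6.10.4.4 lists every type of episode, so no data are lost. This stands in part. However, the general sentence names no hypoglycemia category and no rate, and a listing is not a summary. The condition on severe incidence also appears in Protocol 10.3.4.7, so it is consistent between the documents and is not counted as a gap here. SAP 6.10.3.3 sets a numeric trigger for summarizing SAEs, but 6.10.4.4 does not refer to it.

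**Stronger readings that the documents do not support.**
- *That the rate window is also defective.* A reader might say the plan leaves Visit 801 open. All visits plainly includes it, and its schedule row is marked for the task "Review patient diaries for BG values, AEs, hypoglycemic or hyperglycemic events".
- *That the adverse-event default in SAP 6.10 adds another contradiction.* That default is "AEs summaries will be presented for all postbaseline data". Hypoglycemic episodes go on their own eCRF and are not recorded as AEs unless serious (Protocol 9.2.1.2.4), and 6.10.4.4 sets its own windows. The default does not govern them.
- *That the EAS must be the intended dataset.* It is the only other dataset defined, but choosing it is an inference, and it would itself contradict the closing sentence.

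**Conclusion.** The point holds for overall incidence, for the unnamed dataset, and for the three missing summaries. It does not extend to by-visit incidence or the rate.

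The practical size is unknown, because the documents do not say how many patients stop drug but stay. The 4.3 points per patient assumes an arm of 23 and a patient whose only episode falls after the on-treatment window closes. A reader might infer that one rule would favor or penalize a particular arm. The documents give no basis for a direction.

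The summaries are descriptive, no decision rule rests on them, and the primary HbA1c analysis is unaffected. The correction is still worth making, because the plan cannot be followed as written for these patients and part of a listed secondary endpoint has no table.

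**What to change.** 1. In SAP 6.3, name the population and dataset for hypoglycemia summaries.
2. In SAP 6.10.4.4, reconcile the overall-incidence window with the closing sentence. The sponsor should state which is the main rule. The other may be shown as supportive, since SAP 6.10 already allows that for some key tables "data will be presented both for the treatment period only and for the treatment period and follow-up period combined, if applicable". A second version is optional.
3. Add incidence and rate of documented symptomatic hypoglycemia and a rate of severe hypoglycemia, to match SAP 4.2. Record them as additions to Protocol 10.3.4.7.

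The cost is SAP wording and a few descriptive tables. Some tables will rest on very few events, and if both versions of incidence are shown they must be clearly labelled.
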